9.3. Analysis of Outcome Measures

Control group:

All electrogram samples will be analysed at baseline (long) cycle length and classified as normal or abnormal (see above definitions in section 4). The same sampling points will then be analysed at short cycle length and classified in the same way. The proportion of electrograms changing from normal to abnormal will be recorded as will the change in electrogram amplitude and duration.

The whole chamber mean, median and distribution of voltage amplitude at long cycle length will be analysed. This will also be done for each atrial segment. The segment with the lowest mean amplitude will be identified and the cut-off for the value representing the upper 95% of recordings in that segment calculated. This will be used as the value representing the lower limit of normal for subsequent study analyses.

All participants:

All electrogram samples will be analysed at baseline (long) cycle length and classified as normal or abnormal (see above definitions in section 4). The same sampling points will then be analysed at short cycle length and classified in the same way. The proportion of electrograms classified as normal and abnormal at each cycle length will be calculated for the full sample set and according to baseline electrogram amplitude (<0.5mV, 0.5-lower limit of normal, and >lower limit of normal)(lower limit of normal defined above from analysis of the control group).

For each participant, conduction velocities will be analysed in regions of different baseline electrogram amplitude at both long and short cycle length. This will be done using the Turbomap feature in Precision to create an activation map (specified as measuring on maximum negative dV/dt). Conduction velocity will be calculated as a mean of 5 measurements using the difference in activation times between 2 points in a straight line at set distance through the region of least isochronal crowding. This will be done in regions of low, intermediate and preserved voltage at long and short cycle length.

The outcome measures will be assessed in all patients in whom the study procedure was performed.

Voltage mapping subgroup:

For all maps obtained in this subgroup using both the HD grid and ablation catheter, bipolar voltage amplitudes will be compared. Mean amplitudes will be compared for the entire chamber and each atrial segment (anterior, septal, inferior wall, posterior wall, roof, lateral wall). Each sampling point obtained using the ablation catheter in sinus rhythm/baseline pacing cycle length will then be compared to an equivalent nearest point obtained by the HD grid in sinus rhythm/baseline pacing cycle length to give a difference (+/-) in amplitude recorded. Mean differences will be compared for the whole atrium and each segment as outlined above.

The outcome measures will be assessed in all patients in whom the study procedure was performed.

AcQMap subgroup:

Qualitative and quantitative assessments of conduction patterns identified on AcQMap during AF will be made with regions of frequent focal firing, slow conduction, rotational activation or irregular activation identified (according to AcQTrack and visual interpretation of the operator in line with and according to

their prior experience). Contact electrograms using the HD grid will be recorded at these regions and classified according to their degree of fractionation. Regions identified as above by the operator will be compared to the rest of the atria according to sinus rhythm voltage amplitude and proportional change in electrogram morphology and conduction velocity with changing pacing cycle length.

The outcome measures will be assessed in all patients in whom the study procedure was performed.

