4. OBJECTIVES AND OUTCOME MEASURES

Objectives	Outcome Measures	Timepoint(s) of evaluation of this outcome measure (if applicable)
Primary To define the normal range of voltage amplitude identified using the Abbott EnSite Advisor HD grid (SE) catheter and HD wave solution and response to pacing cycle lengths using a control group with normal	Mean and distribution of left atrial voltage amplitude across the whole chamber and by segments with lower limit of normal defined as the upper 95% value within the segment with the lowest mean amplitude at long pacing cycle length	During ablation procedure

left atria		
Secondary: To characterise the left atrial electrophysiological substrate using electroanatomical voltage and activation mapping using the Abbott EnSite Advisor HD grid (SE) catheter during pacing using a basic cycle length and a single closely coupled extra-stimulus in a cohort of patients undergoing catheter ablation for atrial fibrillation.	A change in electrogram morphology from normal to abnormal (defined as ≥3 deflections lasting ≥50ms) between long and short pacing cycle length in regions of low (<0.5mV), intermediate (0.5-lower limit of normal defined from control group) and normal (defined from control group results) voltage amplitude.	During ablation procedure
	Difference in single vector conduction velocity at long and short cycle lengths in regions of low, intermediate and normal voltage.	During ablation procedure
In a subgroup of 20 patients: To compare electroanatomic voltage mapping (EAVM) performed with a bipolar contact force guided ablation catheter to the Abbott HD grid using orthogonal wave analysis in sinus rhythm.	1. Difference in voltage amplitude by each method in sinus rhythm 2. Surface area and proportion of points of scar (<0.05mV), low voltage (0.05-0.4mV), intermediate voltage and normal voltage (voltage cut-offs defined from control group).	During ablation procedure
In a subgroup of 10 patients: Correlate findings of high density contact mapping with AF propagation patterns using the AcQMap combined imaging and electrophysiological mapping system.	Correlate electrogram amplitude and morphology with regions of uniform, irregular, slow or rotational activation patterns during AF.	During ablation procedure

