To evaluate the distribution of late gadolinium enhancement on cardiac MRI relative to conduction properties identified using the HD grid (as above)	Electrogram amplitude, morphology and conduction velocities at long and short cycle length in regions with and without late gadolinium enhancement on cardiac MRI	During ablation procedure
Correlate dynamic propagation patterns with distribution of atrial scar derived from cardiac MRI	Difference in distribution of late gadolinium enhancement in regions of predominant rotational and irregular activation during AF	N/A

Evaluate the effect of ablation on left atrial scar derived from cardiac MRI	Difference in burden of late gadolinium enhancement on pre-and post procedure cardiac MRI.	3-6 months post procedure
In 5 control patients: Evaluate the effect of cycle length on electrogram morphology in normal subjects	A change in electrogram morphology from normal to abnormal (defined as ≥3 deflections lasting ≥50ms), amplitude and duration between long and short pacing cycle length	During ablation procedure

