7.6. Study visit (control group)

As part of standard care, a 12 lead ECG will be performed for all patients following arrival on the day of their procedure.

Venous access, placement of electrophysiology catheters, and completion of diagnostic electrophysiology study will be undertaken in line with standard clinical care. Trans-septal puncture for left atrial access will be undertaken and anticoagulation will be administered in line with standard protocols. Prior to any ablation, left atrial electroanatomical voltage mapping (EAVM) using the Abbott Advisor HD Grid (SE) mapping catheter using the orthogonal wave setting (HD wave solution) will then be undertaken. This will be conducted during bipolar pacing from the mid point of the coronary sinus catheter at a cycle length of 800ms for 4 beats followed by a single extrastimulus with coupling interval of 300ms. Care must be taken to keep the catheter in each position to record all 5 cycles before moving to acquire new points aiming for a minimum of 300 points in total with full and equal covering of the atrial surface. Interpolation threshold should be set to 7mm with points filtered to within 5mm of the surface anatomy (interior and exterior projection). Initial map collection should be specified as a CFAE map set to collect points with the catheter stationary for 5 seconds.

Following completion of the EAVM, the procedure continues in line with standard clinical practice. If, for any reason the EAVM is not performed then the patient will be removed from the study. If mapping has commenced but is incomplete then the data will still be used.

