9. STATISTICS AND ANALYSIS

9.1. Description of Statistical Methods

This is a mechanistic study exploring a change in electrogram morphology. This will be expressed as a proportion of signals recorded within each amplitude bracket. Statistical comparisons using the chi-square tests of 2 proportions will be made to look for significant differences at long and short cycle length.

In the sub-study comparing voltage mapping methods, simple statistical analysis will be used to compare voltage amplitudes obtained by each method in sinus rhythm and in AF. Means will be compared using independent sample t-test.

Retrospective analyses may be conducted to explore trends in electrophysiological mechanisms identified and their relation to demographic, anatomical, or clinical features recorded and in line with secondary outcome measures.

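### The one-way count of normal-to-abnormal electrogram changes is above zero from classification noise alone, and the plan has no reverse count or noise reference to set against it

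*Combined protocol and SAP*

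**What the plan says.** Section 4 defines the AF-cohort morphology outcome, by voltage bracket, as "A change in electrogram morphology from normal to abnormal (defined as ≥3 deflections lasting ≥50ms) between long and short pacing cycle length". The control-group outcome in the same table is "A change in electrogram morphology from normal to abnormal (defined as ≥3 deflections lasting ≥50ms), amplitude and duration". The control-group paragraph of section 9.3 carries this through: "The proportion of electrograms changing from normal to abnormal will be recorded as will the change in electrogram amplitude and duration".

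The readings are paired. Points are classified at long cycle length first, and "The same sampling points will then be analysed at short cycle length and classified in the same way".

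The all-participants paragraph of section 9.3 adds a different summary: "The proportion of electrograms classified as normal and abnormal at each cycle length will be calculated for the full sample set", and also by baseline amplitude bracket. Section 9.1 expresses the change as a share of the signals within each bracket and names the test: "Statistical comparisons using the chi-square tests of 2 proportions will be made to look for significant differences at long and short cycle length".

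Section 7.6 sets the recording at each site: pacing "at a cycle length of 800ms for 4 beats followed by a single extrastimulus with coupling interval of 300ms". Section 7.7 uses the same sequence for AF patients, with a longer coupling interval where 300 ms does not capture. The plan does not say which of the four 800 ms beats supplies the long-cycle-length reading. It asks for no count of changes from abnormal to normal and no repeatability estimate.

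**The concern.** Abnormality is a threshold on deflection count and duration. A signal near that threshold can fall on either side of it on two successive beats with no change in the tissue. A count of changes in one direction collects these flips and sets nothing against them, so its value under no cycle-length effect is the noise rate and not zero.

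This matters most for the controls. The primary objective includes their response to pacing cycle length, but the primary outcome covers voltage only. For morphology, the normal response therefore rests on the one-way control outcome. If that figure contains an unmeasured noise component, the response of normal atria is overstated by that amount. The section 4 outcome for AF patients has the same property. The AcQMap analysis in section 9.3 may inherit it, because it compares regions on change in morphology without defining change in any other way.

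**Working it through.** The documents state no transition rate, effect size or repeatability figure, so there is nothing of the plan's own to reproduce.

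**Inputs**
- At least 300 points per patient (sections 7.6 and 7.7) and 5 controls (section 9.2): 5 × 300 = 1,500 control points.
- Per-reading misclassification e: an assumption, shown at 2%, 5% and 10%.
- True abnormal prevalence p: an assumption, varied where it matters.

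**1. One-way count under no effect.** The true state is the same on both beats, and errors are independent and symmetric. A point is read normal then abnormal either if it is truly normal and only the second reading is wrong, or truly abnormal and only the first is wrong:

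(1−p)(1−e)e + p·e(1−e) = e(1−e)

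Prevalence drops out. The reverse change has the same probability, so the expected net change is 0.

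| e | e(1−e) | of 300 points | of 1,500 control points |
|---|---|---|---|
| 2% | 1.96% | about 6 | about 29 |
| 5% | 4.75% | about 14 | about 71 |
| 10% | 9.00% | 27 | 135 |

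**2. Errors shared between beats.** If the error indicators on the two beats have correlation r, the expectation becomes e(1−e)(1−r). At r = 0.5 (illustrative) the three values halve to 0.98%, 2.4% and 4.5%. They vanish only at r = 1.

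**3. The marginal comparison.** Each point is read at both cycle lengths, so the abnormal share at short minus that at long cycle length equals (normal-to-abnormal minus abnormal-to-normal) ÷ n. Opposite flips cancel. In 20,000 simulated data sets per setting (1,500 independent paired points; e of 2%, 5%, 10%; p of 5%, 20%; no effect):
- the naive 95% lower limit of the one-way proportion was above zero in every run;
- the two-proportion chi-square on the marginals rejected in 0% to 2.3% of runs, which is conservative because it ignores the pairing;
- McNemar's test rejected in 4.8% to 5.1% of runs.

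Clustering of points within patients was not modelled, so these rejection rates bear only on the noise question.

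**4. With a true effect.** Let the true abnormal share rise from 5% to 10%, with e = 5%:
- normal-to-abnormal: 0.90×0.95×0.05 + 0.05×0.95² + 0.05×0.05×0.95 = 9.0%;
- abnormal-to-normal: 0.90×0.05×0.95 + 0.05×0.05² + 0.05×0.95×0.05 = 4.5%;
- net: 4.5%, against a true 5%.

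The one-way count nearly doubles the true rise; the net slightly understates it.

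**5. Voltage brackets.** With all signals in the bracket as denominator, as section 9.1 indicates, e = 10% gives 9.0% in every bracket whatever the prevalence. Two conditions create a false contrast:
- Unequal error: e of 2% in one bracket and 10% in another gives 1.96% against 9.0%.
- A baseline-normal denominator: at e = 10%, the share read normal is 0.95×0.90 + 0.05×0.10 = 0.86 at 5% prevalence and 0.70×0.90 + 0.30×0.10 = 0.66 at 30%. Then 0.09/0.86 = 10.5% and 0.09/0.66 = 13.6%.

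**The case against.** The strongest reply is that the planned inference is not one-way. The all-participants paragraph gives the shares normal and abnormal at each cycle length, overall and by bracket, and section 9.1 tests long against short. The net change follows from those outputs. This stands: a reader might infer that the plan's significance test turns noise into a cycle-length effect, and it does not.

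The reply extends to the controls. Section 9.2 counts them among the 35 participants, and the schedule of study procedures lists long and short cycle length mapping for everyone. That reading is reasonable but not settled. Section 9.3 gives the controls their own paragraph with a one-way summary, and the all-participants paragraph breaks results down by amplitude, not by group. Even if the controls are included, a net change for them alone is not stated as an output.

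A reader might also infer that noise must favour the intermediate-voltage hypothesis. The documents do not support that. Section 3 mentions some evidence of fractionated signals in intermediate areas, but nothing on how repeatable their classification is, and section 9.1 points to a denominator under which equal error gives equal noise.

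Three further points stand in part. The size is assumed, and holding the catheter still for all five cycles may make errors shared and flips fewer. The control figure is descriptive, with no test against zero. The same definition applies in controls and AF patients, so the control rate is a partial reference for the AF rate, but it mixes noise with any true response in normal atria and so cannot isolate the noise. Finally, net change alone could hide genuine changes in both directions, which is a reason to report the whole paired table.

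**Conclusion.** The point holds for the section 4 morphology outcome, in AF patients and controls, and for the control-group summary in section 9.3. Taken as written, these overstate the response to short cycle length by an amount that the plan does not measure. That amount is 2.0%, 4.8% or 9.0% of all points under no effect for e of 2%, 5% or 10%, assuming errors independent between beats, and less if they are shared. The documents supply no error rate, so the true size is unknown.

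It does not hold for the long-versus-short comparison of proportions in sections 9.1 and 9.3, and a false difference between brackets needs unequal error rates or a baseline-normal denominator. The cancellation in the net change assumes the same error rates at both cycle lengths. In an exploratory study with a descriptive control result this is a modest defect, worth correcting because the data to correct it are already recorded.

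**What to change.** In sections 4 and 9.3:
- Report the paired 2×2 table (normal-to-abnormal, abnormal-to-normal and net change) for the controls as a group and for each voltage bracket, with all signals in the bracket as the stated denominator.
- Base the interpretation of the cycle-length effect on the net change. Any test of it should respect the pairing and allow for clustering of points within patients.
- Prespecify which 800 ms beat gives the long-cycle-length reading and which second 800 ms beat is the repeat. Report the same one-way count between those two beats, by group and bracket, as the noise reference.
- State whether the all-participants analysis includes the controls.

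The cost is one extra beat classified per site from existing recordings, and a few sentences of text. No additional mapping, procedure time or patients are needed.

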EAVM may significantly underestimate fibrosis when compared with MRI. One MRI study found >20% atrial fibrosis in 51% of patients and a second study found >10% fibrosis in 81%.(14, 15) Rolf's study assessing ablation of low voltage areas found these to be present in only 26% of patients.(7) This suggests that current strategies of EAVM fail to detect a significant proportion of fibrosis seen in MRI. This may be the result of regions of patchy fibrosis with relatively preserved voltage amplitude but abnormal conduction properties, important for AF propagation.

Studies have shown an increase in total atrial conduction time with increasing duration of AF and a corresponding slowing in conduction velocity.(10) Conduction velocities are significantly reduced in low voltage areas (<0.5mV) but are less thoroughly studied in regions of intermediate voltage.(16) Furthermore, the majority of this work has been undertaken in sinus rhythm. Conduction velocity and refractoriness are significantly affected by the interval between successive beats. Ectopic (premature) beats, usually originating in the pulmonary veins, commonly trigger AF. Therefore, although resting atrial conduction properties (and electrogram morphology) may appear normal, response to closely coupled ectopic activation could be impaired and contribute to the initiation and maintenance of fibrillation.

EAVM during AF is influenced by the effect of wavefront directionality on bipolar electrogram amplitude. The novel Abbott EnSite Advisor HD grid (SE) catheter uses orthogonal bipoles to reduce the

effect of wavefront direction (HD wave solution) and is therefore designed to facilitate more accurate substrate assessment compared to conventional bipolar mapping catheters. Appropriate voltage amplitude values representing the cut-off between normal and abnormal will vary with the catheter used (the result of electrode size and spacing) and has not been clearly defined with this technology.

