9.2. The Number of Participants

The total number of participants will be 35; 30 with AF and 5 controls. Previous studies have revealed the presence of low voltage areas (<0.5mV) in approximately 35% of patients with persistent AF undergoing catheter ablation,(7) and in the one previous prospective study of patients without low voltage areas, intermediate amplitude regions were observed in 43%.(9) Our hypothesis is that conduction properties, and thus electrogram morphology will become abnormal at shorter cycle length. A sample of 35 is consistent with previous mechanistic exploratory studies and should include enough patients with regions of voltage amplitude <1.1mV according to prior results outlined above and allow comparisons between each cycle length. As this is an exploratory study we are not evaluating a specific intervention, formal power calculations have limited usefulness.

The control group will consist of 5 patients with presumed normal atria. Although this is a small number, a high number of points will be collected to allow good distribution of results. By analysing the combined total electrogram recordings and excluding patients with any risk factors for abnormal atrial substrate then this sample should provide adequate estimation of normal values.

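### The morphology analysis uses each point's measured amplitude only as three brackets, and the upper edge is a single tail value from 5 controls treated as known; a continuous-amplitude model and alternative edges should be added.

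*Combined protocol and SAP*

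**What the plan says.** Section 9.3 (all participants) classifies every electrogram as normal or abnormal at long cycle length and again, at the same points, at short cycle length. The proportions are then calculated for the whole sample and "according to baseline electrogram amplitude (<0.5mV, 0.5-lower limit of normal, and >lower limit of normal". Section 9.1 says of the change in morphology: "This will be expressed as a proportion of signals recorded within each amplitude bracket". It names a chi-square test comparing long with short cycle length.

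The lower edge, 0.5 mV, is fixed in advance. The upper edge comes from the control part of section 9.3: the segment with the lowest mean amplitude is found and "the cut-off for the value representing the upper 95% of recordings in that segment calculated". Then: "This will be used as the value representing the lower limit of normal for subsequent study analyses". On numbers, section 9.2 states: "The control group will consist of 5 patients with presumed normal atria". It calls the sample adequate on this ground: "By analysing the combined total electrogram recordings and excluding patients with any risk factors for abnormal atrial substrate". Each control map is collected "aiming for a minimum of 300 points in total with full and equal covering of the atrial surface" (section 7.6).

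Section 3 says that the voltage separating normal from abnormal "will vary with the catheter used (the result of electrode size and spacing) and has not been clearly defined with this technology". It also reports that earlier work took normal as above 1.1 or 1.3 mV. Its hypothesis is that intermediate-voltage regions respond more strongly to a shorter cycle length than regions of preserved amplitude.

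For morphology, the documents specify no analysis on continuous amplitude, no interval for the lower limit of normal, and no repeat with another limit.

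**The concern.** Two features combine. First, a point just above 0.5 mV and a point just below the limit are treated as alike, while two points just either side of the limit are treated as different, although the amplitude of all four is known. Second, the limit that separates intermediate from normal is an estimate from 5 people, yet it is used as if it were known.

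That boundary is the one the hypothesis in section 3 turns on. If the limit is too high, ordinary points enter the intermediate bracket. If it is too low, affected points enter the normal bracket. If it falls at or below 0.5 mV, the intermediate bracket is empty, and the plan does not cover that case. A reader of the bracket table could not tell how far the result reflects tissue and how far it reflects where the limit fell.

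**Working it through.** The plan gives no alpha, power, effect size, standard deviation or amplitude distribution, so it has no figure of its own to reproduce. The check has three parts.

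**1. How many recordings and people fix the limit.** Inputs: 5 controls (section 9.2), at least 300 points each (section 7.6), and the six segments that section 9.3 names for the voltage subgroup. Assumptions: the same six segments serve the controls, points are spread evenly, and the limit is the value that 95% of recordings exceed, that is, the 5th percentile.

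- Points per control per segment: 300 / 6 = 50.
- Pooled points in the lowest-mean segment: 5 × 50 = 250.
- Points below the limit: 0.05 × 250 = 12.5.

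One control contributes 50 of the 250 points, so a single heart with low amplitudes could supply all 12 or 13 values that set the limit. More points per heart do not reduce variation between hearts.

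**2. How imprecise the limit could be (illustration).** Simulation of 5 controls × 6 segments × 50 log-normal points. Assumptions, none from the documents: chamber median 2.5 mV, segment shifts of −0.3 to +0.2 on the log scale, within-patient log SD 0.5, and a patient effect with the log SD shown plus a patient-by-segment effect of half that SD.

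| Between-patient log SD | Median limit (mV) | 95% range of limit (mV) |
|---|---|---|
| 0 | 0.82 | 0.72 to 0.93 |
| 0.2 | 0.77 | 0.59 to 0.99 |
| 0.4 | 0.67 | 0.39 to 1.05 |

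The range widens with between-patient variation, which pooling points leaves out of account. Over all the settings tried (median 1.5 or 2.5 mV, within-patient log SD 0.5 or 0.7), the chance of a limit at or below 0.5 mV ran from 0% to 100%. That span shows only that the answer depends on unknown inputs.

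**3. What the limit does to the intermediate bracket (illustration).** Assume AF amplitudes are log-normal with median 1.5 mV and log SD 0.8. The intermediate share for a limit L is

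Φ[ln(L/1.5)/0.8] − Φ[ln(0.5/1.5)/0.8].

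- Share below 0.5 mV: Φ(−1.373) = 0.085, whatever the limit.
- L = 1.1 mV: Φ(−0.388) − 0.085 = 0.349 − 0.085 = 0.264.
- L = 1.3 mV: Φ(−0.179) − 0.085 = 0.429 − 0.085 = 0.344.

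Moving between the two limits cited in section 3 reclassifies 34.4% − 26.4% = 8.0% of points. If each of the 30 AF patients gave 300 points, that is 0.080 × 9,000 = 720 points. With the limits from the last row of the table, 0.39 and 1.05 mV, the intermediate share would run from 0% (bracket empty) to about 24%.

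**The case against.** The strongest reply is that the brackets are the point of the study. Establishing this catheter's lower limit of normal is the primary objective, the section 3 remark on undefined cut-offs is the reason for deriving one, and the hypothesis is worded as a comparison of intermediate with preserved regions. This stands: the brackets belong in the results and should not be demoted. It does not answer the uncertainty in the limit, and a continuous model does not make 5 controls more informative. The model only gives a result that does not depend on that one value.

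A second reply is that dependence on the limit is partial. This also stands. The full-sample proportion is free of it, 0.5 mV is prespecified, and the only named test compares cycle lengths. The study calls itself exploratory, and section 9.1 allows retrospective exploration, though it does not mention amplitude as a continuous variable.

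Three stronger readings are tempting, and the documents do not support them.

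- A reader might infer that the hypothesis is a gradient, with more change the lower the voltage. Section 3 states a contrast of categories. It also links fractionation in intermediate areas to patchy enhancement as opposed to dense fibrosis, so a non-monotone pattern is plausible.
- A reader might quote a percentage of information lost. Under the distribution in part 3, the brackets keep 67% of the variance of log amplitude at 1.1 mV and 72% at 1.3 mV. Those figures measure efficiency for a linear trend, which the plan does not test. They run from about 20% to 80% as the assumed median (1.0 to 2.0 mV), log SD (0.6 to 1.0) and limit (0.7 to 1.3 mV) vary.
- A reader might extend the point to conduction velocity. Section 9.3 takes velocity as a mean of 5 measurements in each low, intermediate and preserved region, so there is no velocity per point to model against amplitude.

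**Conclusion.** The point holds for the morphology outcome. Measured amplitude is used only as three brackets, and the upper edge is a tail value pooled from 5 controls and treated as exact. No analysis shows whether the intermediate-versus-preserved result survives a different edge.

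The documents do not allow the effect to be sized. The shares of 26% and 34%, and the simulated ranges for the limit, rest on assumed log-normal distributions and show only that the bracket can change materially. The limits of 1.1 and 1.3 mV come from earlier work with varying technology, so they are reference values for a sensitivity analysis and not claims about this catheter. The direction needs no such assumption: the contents of the two upper brackets change with the limit. This is an inexpensive improvement to an exploratory analysis and does not invalidate the planned one.

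**What to change.** In section 9.3, keep the three-bracket morphology results as planned and add, for morphology only:

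- A mixed logistic model of normal or abnormal status on cycle length, a spline in log amplitude at long cycle length, and their interaction, with patient as random effect. Each point is classified twice, so the text should also say how that pairing enters the intervals.
- The predicted change in the probability of an abnormal electrogram from long to short cycle length, with confidence interval, at 0.5 mV, at 1.1 and 1.3 mV, and at the control-derived limit.
- A repeat of the bracket results with 1.1 and 1.3 mV as the upper edge.

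Leave the regional conduction-velocity analysis as it is. No new data, patients or procedures are needed. The cost is some SAP wording, modest extra analysis, and a curve reported beside the table.
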